Oversight: [name], the Principal Investigator, will administer the Data Safety Monitoring Plan for this project and report all results of the yearly reviews to University of Texas IRB and the NIH Project Officer. Events specifically examined will include (but are not limited to) psychiatric hospitalization, suicidal attempts, and abuse. No planned interim statistical analyses will be performed, though the occurrence of events by condition will be examined in tabular form. Should trends become apparent

that indicate the potential for significant imbalance by condition, a special board will be convened to review the data and make a recommendation as to the disposition of the trial. Any action that results in the temporary or permanent suspension of the project will be undertaken with consultation with the study's NIH project officer and the University of Texas IRB.

The University of Texas is responsible for the general oversight for all grants. Each study is reviewed yearly by the IRB during the regular continuing review process, outlining the following points:

- Reassessment of the risks and benefits to study participants
- Participant recruitment, accrual, and retention
- Confidentiality
- Consideration of external scientific or therapeutic developments with impact on the safety of participants
- Review of adverse events The PI will update the general DSMP procedures as needed.

Statistics

- This study was designed around the maximum sample size possible given the logistical limitations of the study (time, expense). For a total sample size of 25 subjects (Aim 3, the power associated with any of the independent effects in any of the proposed statistical models will be approximately 80% (P value cutoff = .01) as long as the effect accounts for 3% of the total variance relative to the model specific error term (i.e., $R^2 = .03$). This will be true for any effect that is included in any of the statistical models either pre or postoperative and includes both main effects and possible interactions. The power will change slightly due to the complexity of the model and the number of independent effects included, but overall, considering the tradeoff between increased efficiency and loss of error degrees of freedom in more complex models, the power will remain at approximately 80% when 3% of the variance is explained. This axiom also holds no matter the scale of measurement (i.e., continuous or discrete). An R^2 of .03 equates to a "d" statistic (i.e. Cohen's d) of approximately .35. According to Cohen's taxonomy for the social sciences, this is a small to medium effect size. Effects accounting for less than 3% of the total variance are most likely of limited clinical significance. As previously stated in the statistical methods, considering the observational nature of the investigation, we have chosen to use a more conservative P value cutoff. More importantly this conservative standard also increases the chances of reproducibility and helps to account for the amount of statistical modeling/testing that increases the likelihood of irreproducible results.

Ethics

- For all study participants the initial consent process will take place during recruitment process by clinical staff and research staff. However, if a willing participant does not have time to learn about, and sign all consent forms, study staff will schedule a follow up time with them to consent. If needed participants will be allowed to take consent home to review before speaking to research staff or clinical staff administer consent.

Data handling and record keeping

- Quality control and assurance.* Data storage and management will be accomplished via FileMaker Pro, a cross-platform object-oriented relational database application. Our database manager will be responsible for the development, security, backups, audit logs, and managing database user access. Regarding data/records confidentiality, we have an established set of procedures designed to ensure the protection of confidentiality. All records on active participants will be stored in locked file cabinets in the office of the Principal Investigator, who will maintain strict control over these records. As in our other studies, we will use a record system in which all participant records are filed numerically by case number, with no names attached to the database. Access to the database and data files is strictly controlled by the Principal Investigator. Passwords are used to restrict entry into the database. Project staff is specifically trained on issues of confidentiality. Facilitators will also be trained on issues of confidentiality.
- Filemaker Data Management Platform.* The database manager will develop a web-based relational database using FileMaker Pro, a secure cross-platform object-oriented relational database application for electronic collection and management of research and clinical study data. The database design will replicate the proposed data collection forms and will be developed in accordance with necessary security, compliance, and study requirements, with oversight from the study's PI. The data collection team will be able to enter data into the database through a secure website. Access to and user privileges within the database will be managed using the UT single sign-on(SSO).

Quality control and assurance

- Quality Assurance: Accuracy and Completeness of the Data during Data Collection, Entry, Transmission and Analysis.* The project lead coordinator will be entrusted with scanning spot check 10% of the data after entry to ensure accuracy and check questionnaires for completeness as they are collected. Field team staff will follow-up with study participants and concerning questions that are skipped. Participants are allowed to decline to answer, but data checking is in place to ensure that data is not missing due to unintended circumstances.
- Data Integrity:* To maintain data integrity, fields within the FileMaker application will have data type validation, simple ranges, and/or constraints. Data type validation will check that the entered data fits into the field type (e.g. a date field only accepts data entered in a date format). Simple ranges ensure that the data entered fits within the minimum and maximum values. Constraints check for invalid characters or values. Additionally more advanced checks can be done, such as cross-reference and structured validations. Additionally, ad-hoc reports can be generated to check for data accuracy during the data collection process. Access to this feature will be restricted to required users using user privileges.

- *Data Export for Analysis:* Data can be exported out from FileMaker in various ways and in various formats. Data may be exported as a CSV (comma-delimited) file from a report or as a PDF file from the data entry page when viewing a particular record. Additionally, all collected data can be exported to CSV, XML, DBF, or Microsoft Excel file types. Other database management systems and/or statistical software, such as SAS or SPSS can interface via open database connectivity (ODBC). This interface allows for direct data importing, running SQL queries, generating ad-hoc reports, and accessing the data in real time. Access to these features will be restricted to authorized users using user privileges.
- *Data confidentiality, Storage and Preservation:* At the completion of the data collection process, access to the database by the data collection team will be disabled. Study coordinators and the PI will continue to have access for any required data cleaning. At the completion of the proposed study, access to database will be removed for all nonessential team members and further data modification will be disabled. All data will then be transferred from the database server into a 256- bit AES encrypted archive file and will only be accessible to the PI and a secondary co-custodian. All participants will be assigned a unique code number by PI [name]. This ID number will be used on all response forms, spreadsheets and data files to ensure participant confidentiality. Participant name, address, telephone, and any other means of identification will be destroyed following the completion of data collection using methods described by the IRB. All study personnel are equipped with password protected personal computer access and password protected access to a network drive accessible only from project staff computers. All computers and network drives are maintained by UT Health's Information Technology Department (IT).
- **Data Security.** For added security and reliability, the FileMaker environment is separated into two servers, a web server and a database server. Data entry is done through the web server only and users do not have direct access to the database server. All transmitted data is encrypted using HTTPS and Secure Socket Layer (SSL) encryption, to maintain secure communication from the user to the web server. All incoming data is then sanitized and stored using AES-256 encryption on the database server. Both servers will be managed by UT Health's Information Technology and are physically located at its data center and covered by its security policies. Which include continuous network scans, penetration testing, daily patches, off-site tape backups, and other enterprise-level data management procedures. Additional security is implemented at the application level. FileMaker maintains a built-in audit trail that logs all events, user access, and data creation and modifications. Log files can be exported for analysis and reporting purposes. All collected data is backed up hourly with redundant nightly backups stored to a separate server going back 6 months. Database consistency checks for errors and server maintenance also occur daily.
- Finally, a Data Safety Board will monitor all adverse events. Possible adverse events include those cases identified above as well as emotional distress associated with assessment or study participation. Adverse events will be reported to the chair of the committee as soon as possible and no later than 24 hours after they occur. Appropriate measures will be taken to ensure the participant's safety including referrals to primary care physician or supportive counseling provided by intervention staff. A summary of all adverse events will be sent to the chair of the Data Safety

Board every month. At least monthly, the Data Safety Board will review all adverse incidents via a face-to-face meeting. This committee will have the power to suspend recruitment to the study or discontinue the study entirely if they have concerns about the safety of the participants or the study itself.

Publication Plan

- Results from this study will be published in leading peer-reviewed journals. The PI anticipates a minimum of 6 final published manuscripts. These aggregate results will be available to research subjects and they will be made aware of their existence.

References

2. [name] SE, Xie L, Atem F, Mathew SM, [name] F, Schneider BE, Muñoz NC. Disparity Between United States Adolescent Class II and III Obesity Trends and Bariatric Surgery Utilization, 2015- 2018. *Ann Surg*. 2020 Sep 15. doi: 10.1097/SLA.0000000000004493. Epub ahead of print. PMID: 32941272.

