
Objectives

[figure not shown]
- We will examine how lifestyle interventions combined with bariatric surgery over time can optimize treatment outcomes via the following aims:
- AIM 1.** Generate qualitative data *necessary to adapt* an existing evidence-based healthy lifestyle behavioral intervention's content, strategies and delivery methods to explicitly support pre- and post-MBS, ethnically diverse (non-Hispanic white and black; Hispanic, other), adolescent patients and their families. This formative research will include focus groups, and key informant interviews with adolescents, parents, and clinical team members.
- AIM 2.** *Adapt* the healthy lifestyle behavioral intervention (referenced in AIM 1), as informed by AIM 1 data (and analyses), to support pre-and post-MBS among ethnically diverse adolescent patients and their families.
- AIM 3.** Conduct a *proof of concept study* to assess feasibility, acceptability, and effectiveness of an MBS-supported healthy lifestyle behavioral intervention (*adapted* in AIM 2) among adolescent patients, their families, and their clinical team. Compare social determinants of health (SDOH) screening data with a comparable adolescent patient population from Children's Health.

Hypothesis₁: Acceptability and feasibility (adoption) of an adolescent-targeted multimedia lifestyle intervention sequenced with bariatric surgery with improve 3-and 6-month post-operative health-related outcomes.

Study Design

- This study will employ a mixed-methods design; AIM 1 will focus on qualitative data collection to inform adaptation of the intervention (AIM 2) and AIM 3 will conduct a pilot of the adapted intervention.

Figure 2. Study Schematic Adapted from the Obesity-Related Behavioral Intervention Trials (ORBIT)³³ that focuses exclusively on the early, pre-efficacy phases of behavioral treatment development.

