- **AIM 3. Pilot test of the MBS-supported intervention.** Based on work completed in study AIMS 1 and 2 we will conduct a 9-month pilot test of the MBS-supported intervention in AIM 3 among 20 adolescent patients meeting MBS/NIH qualifying criteria¹⁰ (class II obesity/120% of the 95th percentile and a co-morbidity, or class III obesity/140% of the 95th percentile according to CDC's age-and sex matched growth charts). Subjects will be enrolled up to 3 months (and not < 1 month) pre-MBS and for 6 months post-MBS. We will provide a water bottle at their first clinic visit. Upon completion of the surgery participants may receive a FitBit, a smart scale, workout bands, and weights to aid in their weight loss journey. *Recruitment.* Recruitment will take place in the outpatient suites of either the COACH or MBS Clinics which are located in the Children's Ambulatory Pavilion adjacent to the Children's Health (CH) System of TX main hospital. The COACH clinic currently has a waitlist of over 200 patients for obesity treatment programs and > 50% qualify for MBS. A total of 234 patients < 18 years old have been referred to MBS from 2016 to 2019.⁹²
- **Intervention Delivery.** After patient/parent consent is completed, participants will begin the pre-MBS intervention phase. A *minimum of 6 online sessions will occur pre-MBS, and 20 will occur post-MBS.* [name], MBS coordinator and a diabetes educator in Co-I [name]/[name]'s clinic will manage session delivery to adolescents/parents. All content will follow the DPP-adapted curriculum flow. After The RA will perform outreach, reminder calls, and follow-up for missed surveys or online content. Pre- and post-MBS intervention delivery (based on adapted curriculum/model) may consist of a combination of 1-on-1 and group sessions (in-person or virtually), and online support tools, dependent upon adolescent/parent qualitative feedback on delivery method preference.

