- **Measures.** We are including (1) demographic (age, sex, race/ethnicity, living situation, etc.), (2) anthropometric and cardiometabolic (lipids, insulin, glucose, blood pressure, HbA1c) (**Table 2**); (3) health-related quality of life (HRQOL)⁹³; and (4) process measures (feasibility, acceptability of intervention content/delivery, guided by the RE-AIM [Reach, Efficacy, Adoption, Implementation, Maintenance] framework⁹⁴⁻⁹⁶) in the proposed study. We will also include standard-of-care pre-post MBS physical activity (past 7-day step counts, 24-hour diet recall assessments and the Family Assessment Device-12 item (parent and adolescent report of affective responsiveness and involvement, and problem solving within one's family); Clinical Measures. Anthropometric and cardiometabolic data will be collected at baseline and at 3- and 6-months post MBS as part of standard of care. All blood samples are documented in the Electronic Health Record. HRQOL. At 1 month pre- and 6-months post-MBS, we will administer the CDC's HRQOL-14 Healthy Days Measure. This survey includes 3 modules (Healthy Days Core Module = 4 questions, Activity Limitations Module = 5 questions, and the Healthy Days Symptoms Module = 5 questions). This instrument has been validated in the study age group.⁹⁷ SDOH. Literacy, social, food, driving, financial, and housing needs, and tobacco use.
- **Process Measures.** Qualitative/quantitative process measures will be collected across all intervention sessions via embedded short surveys and at 6-months post-MBS to assess: acceptability (content was appropriate, interesting, easy to use), feasibility (recruitment, retention & adherence rates), and sustainability (perceived barriers/facilitator to intervention implementation, strategies) of the lifestyle intervention. All process measures will be guided by the RE-AIM framework which is particularly appropriate for assessing the fit and relevance of interventions in real-world settings.⁹⁴⁻⁹⁶

The PI has integrated RE-AIM in her past obesity work.^{31,98}

- **Data Analysis Plan.** The AIM 3 dependent measure for each dependent effect will be based on the change from pre to post-MBS weight loss cardiometabolic resolution measurements (**Table 2**). Proportions and means will be the primary scales of the dependent outcomes used to evaluate Table

Table 2. Anthropometric and Cardiometabolic Outcome Measures	
Anthropometrics	Instrument

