(1) Raw Weight Loss	Digital scale (to nearest 0.1 pounds) with the participants wearing light clothing, no shoes.
(2) Body Mass Index (BMI)	Digital scale and height (to nearest 0.5 cm, via Accustat Genentech stadiometer)
(3) Excess Weight Loss (EWL)	Pre-MBS weight - follow up weight)/(Pre-MBS weight - ideal body weight) × 100%

2 outcomes. We will use the Generalized Linear Model (GZLM) to model the impact of the intervention developed in AIM 2 for dependent effects.

Much like the General Linear

(4) Body Composition	InBody570 body composition analyzer- muscle, fat and total body water measures
Comorbidity Resolution	
(1) Cardiometabolic Profile	lipids, insulin, glucose, blood pressure

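### Hypothesis 1 credits adoption of the programme, but no specified analysis links adoption to outcome, and the pre-post tests cannot separate programme from surgery

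*Combined protocol and SAP*

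**What the plan says.** **Hypothesis.** The Objectives section states one hypothesis: "Acceptability and feasibility (adoption) of an adolescent-targeted multimedia lifestyle intervention sequenced with bariatric surgery with improve 3-and 6-month post-operative health-related outcomes". Read literally, the factor said to drive the outcomes is acceptability and adoption.

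**Data.** Study Measures, under Process Measures, plans to assess "acceptability (content was appropriate, interesting, easy to use), feasibility (recruitment, retention & adherence rates". It adds that "process measures will be collected across all intervention sessions via embedded short surveys and at 6-months post-MBS". Intervention Delivery supplies a planned dose: a "minimum of 6 online sessions will occur pre-MBS, and 20 will occur post-MBS".

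**Analysis.** The Data Analysis Plan says: "The AIM 3 dependent measure for each dependent effect will be based on the change from pre to post-MBS weight loss cardiometabolic resolution measurements". It continues: "We will use the Generalized Linear Model (GZLM) to model the impact of the intervention developed in AIM 2 for dependent effects". The terms it names are the repeated time points (pre-surgery, 3 and 6 months) and baseline measures as covariates. Change in weight goes to a Hotelling T² test at a 1% level. The power paragraph for AIM 3 describes a single-factor repeated-measures design.

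**Design.** According to Study Design, AIM 3 enrols adolescents who have already decided to have surgery, and follows them for 6 months after it. All are to receive the programme. The one comparison with outside patients, in Objectives and Study Procedures, concerns social determinants of health.

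**The concern.** The hypothesis makes a claim about adoption, while the named tests ask whether weight and cardiometabolic measures change from before surgery to after it. No intervention, adoption, adherence or acceptability variable is defined for the model, although the model's stated purpose is "to model the impact of the intervention developed in AIM 2 for dependent effects".

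The Background section describes surgery as effective in this age group, so a marked pre-post change is expected from surgery alone. If the plan is followed as written, that change is the only inferential result to set beside Hypothesis 1, and it would be presented as the impact of the programme. Study Design also promises information on what the intervention contributes to weight loss, and Study Procedures intends to use medical records to judge its effectiveness. Neither gives a method. Meanwhile the data that bear directly on adoption would have no stated role in the analysis.

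**Working it through.** **1. Hypothesis, data and analysis side by side**

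| Element of Hypothesis 1 | Collected? | Used in a specified analysis? |
|---|---|---|
| Acceptability | Yes, session surveys and 6 months post-surgery | None specified |
| Feasibility or adoption (recruitment, retention, adherence) | Yes | None specified |
| 3- and 6-month outcomes | Yes, Table 2 measures | Yes: T² test and generalized linear model, change over time |
| Link from adoption to outcome | Could be built from the rows above | None specified |
| Programme separated from surgery | No: all are to receive both | Not possible in one group |

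**2. What the plan's own power figure covers**

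Inputs from Statistical Power for AIM 3: n = 20, alpha = 0.01, SD = 1, all correlations 0.25, contrast = 1, stated power 80%.

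- The two differences from baseline each have variance 2(1 − 0.25) = 1.5 and covariance 1 − 0.25 = 0.75.
- With means (0, 1, 1), the squared distance d′V⁻¹d is 2/2.25 = 0.889. Means (0, 0, 1) give the same: 1.5/1.6875 = 0.889.
- Noncentrality = 20 × 0.889 = 17.78. The 1% critical value of F(2, 18) is 6.01. Power = **78.9%**, close to the stated 80%.

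The contrast coefficients are not given, so the match depends on the reading; linear means (0, 0.5, 1) give 62.8%. Under any of them, the only effect in the calculation is time.

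**3. The second power statement does not cover an adherence term**

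The Statistics section claims about 80% power for any effect in any model with N = 25, alpha 0.01 and R² = 0.03. For a one-degree-of-freedom F test, noncentrality = 25 × 0.03/0.97 = 0.773, and the 1% critical value of F(1, 23) is 7.88. Power is **4.0%**, and about 381 participants would be needed for 80%. This statement cannot be relied on to show that an added adherence term would be adequately powered.

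**4. What an adherence-outcome model could detect**

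Take a regression of the 6-month outcome on the pre-surgery value and sessions completed before and after surgery. Each session term is then adjusted for two others. With 20 participants analysed and 80% power, Fisher's z gives

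r = tanh[(z₁₋α/₂ + z₀.₈₀)/√(n − 3 − 2)]

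- alpha 0.01: tanh(3.417/√15) = **0.71**
- alpha 0.05: tanh(2.802/√15) = **0.62**

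Without the two adjusting terms, √17 replaces √15 and the values are 0.68 and 0.59. The documents give no expected adherence effect. Over an assumed range, a single-predictor F test at n = 20 and alpha 0.01 has power 10% for r = 0.3, 41% for r = 0.5 and 68% for r = 0.6.

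**5. What the feasibility rates could show**

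The plan expects about 10% attrition and recruits 22. If 20 of 22 are retained, the rate is 20/22 = 91%. The exact 95% interval, from the 2.5% quantile of Beta(20, 3) to the 97.5% quantile of Beta(21, 2), is **71% to 99%**. That is wide, but it addresses feasibility directly.

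**The case against.** The strongest reply is that the hypothesis sentence is garbled and should not be parsed so closely. AIM 3, just above it, sets out to assess feasibility, acceptability and effectiveness. The sentence may simply mean that an acceptable, feasible programme combined with surgery improves outcomes, in which case the pre-post test is the intended one. That reading is plausible, but it does not rescue the test: with no comparator and surgery planned for everyone, improvement after surgery is not evidence for the programme.

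A second reply is that this is a small pre-efficacy pilot, and that feasibility rates are already to be assessed under RE-AIM. This is partly right. Collection is planned; what the Data Analysis Plan lacks is any denominator, interval or summary for these rates.

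A third is that a regression on attendance in 20 adolescents would be confounded and weak. That stands, and it is why the regression is only optional.

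A reader might also infer more than the documents support:

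- *That the data cannot support or refute the hypothesis.* Acceptability and adherence are collected, so an association could be estimated. The analysis is missing, not the data.
- *That the plan excludes an adherence term.* The model's independent variables are never fully listed, and the Statistics section allows for main effects and interactions. The documents show only that no such term is specified.
- *That the test result would be unaffected by attendance.* If attendance influences weight, the result would change. The point is that the tests do not use attendance.

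**Conclusion.** The concern holds in this form: no specified analysis connects the collected acceptability and adherence data to any outcome, and the pre-post tests cannot separate the programme from surgery. Neither the literal nor the looser reading of Hypothesis 1 can be tested by the analyses named. The change should be made, because a result expected from surgery alone would otherwise be labelled as the programme's impact.

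The conclusion rests on the text and the single-group design, not on a numerical error. The detectable correlations of 0.71 and 0.62 do not measure the defect. They show that the optional remedy could find only a very strong association, assuming 20 participants analysed, two adjusting terms and approximate normality. A regression on attendance would not isolate a programme effect either.

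**What to change.** 1. **Objectives.** Restate Hypothesis 1 as a statement about feasibility and acceptability. Report recruitment, retention, adherence and acceptability as rates with exact confidence intervals over all enrolled (for recruitment, over all approached). Define adherence against the planned sessions, separately before and after surgery.
2. **Data Analysis Plan.** State that pre-post change describes programme plus surgery, and that a significant T² or model result is not by itself evidence for Hypothesis 1 or for the programme's impact. Amend the sentence on modelling the intervention's impact to match.
3. **Optional.** Add an exploratory regression of the 6-month outcome on the pre-surgery value plus sessions completed before and after surgery, or plus an acceptability score. Report an estimate with an interval, not a pass/fail test.

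Items 1 and 2 cost rewording and a short table. Item 3 costs one model on data already planned. Its drawbacks should be stated alongside it: it is observational, confounded by motivation, imprecise, and open to reverse causation, because post-surgery sessions accrue while weight is already changing and early weight response may affect attendance.
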